9.2 Publication of results

Any formal presentation or publication of data from this trial may be published after review and comment by Novartis and Celgene Corporation and prior to any outside submission. Novartis and Celgene Corporation must receive copies of any intended communication in advance of publication (at least fifteen working days for presentational materials and abstracts and thirty working days for manuscripts). These requirements acknowledge Celgene Corporation and Novartis' responsibility to provide peer input regarding the scientific content and conclusions of such publications or presentations. Principal Investigation/Institution shall have the final authority to determine the scope and content of its publications, provided such authority shall be exercised with reasonable regard for the interests of Novartis and Celgene Corporation and, in accord with the trial contract and shall not permit disclosure of Novartis and Celgene Corporation confidential or proprietary information.

9.3 Data Monitoring Committee

The institution data safety monitoring committee will review the outcome of the study at regular intervals as mandated by institutional policy or more frequently if deemed necessary by the Principal Investigator. The Data Monitoring Committee (DMC) will be composed of medical and statistical independent reviewers and will meet to review the efficacy and safety data and determine a risk/benefit analysis in this subject population. The purpose of the DMC is to advise on serious safety considerations, lack of efficacy and any other considerations within the charge to the Committee. The DMC may request additional meetings or safety reports as deemed necessary upon discussion with Celgene and its representatives. The DMC may stop the study following review of results from each interim analysis. Appropriate efficacy and safety data summaries will be provided to the DMC after each interim analysis.

In addition, the principal investigator will review the toxicities as they occur and/or are reported. The approval of the principal investigator or designee is necessary for accrual of all patients. Toxicity information will be reviewed at the weekly Phase I meetings attended by all PIs, clinical coordinators and research nurses involved in all ongoing phase I clinical trials at WCI. If the data review reveals a change in the risk/benefit ratio, the investigator will notify the IRB. The principal investigator and co-investigators will review the data and forward any changes or protocol amendments to the IRB. All serious adverse events will be immediately reported to the IRB as outlined in the full protocol. All study participant information will be kept in a confidential manner by the assigning of a random number to each study participant. All data will be kept confidential as per institutional guidelines and policies. Any breach of confidentiality is a serious matter and conflicts with institutional policies and will be reported to the IRB. A cumulative summary of all adverse events occurring on this study and a report of the data safety and monitoring plan will be submitted to the IRBs with the annual renewal reports.

9.4 Study auditing

9.4.1 Investigator responsibilities

Investigator responsibilities are set out in the ICH guideline for Good Clinical Practice (GCP) and in the US Code of Federal Regulations.

Investigators must enter study data onto CRFs or other data collection system. The Investigator will permit study-related audits by Celgene or its representatives, IRB/EC review, and regulatory inspection(s) (e.g., FDA, EMEA, TPP), providing direct access to the facilities where the study took place, to source documents, to CRFs, and to all other study documents.

The Investigator, or a designated member of the Investigator's staff, must be available at some time during audits to review data and resolve any queries and to allow direct access to the subject's records (e.g., medical records, office charts, hospital charts, and study related charts) for source data verification. The data collection must be completed prior to each visit and be made available to the Celgene representative so that the accuracy and completeness may be checked.

10 Biostatistical Analysis

10.1 Overview

All data will be listed individually by subject. Continuous variables will be summarized using descriptive statistics: mean, standard deviation, median, and minimum and maximum values. Categorical variables will be summarized using number of subjects and proportion expressed as percentage. Baseline value for any specified variable is the last valid measurement before the administration of the study drug. Unless otherwise indicated, statistical significance will be declared if the two-sided p value is ≤ 0.05 .

10.2 Datasets to be analyzed

Demographics

Subject demographics including age, sex, race, ethnicity, height, weight, disease information, and medical conditions will be summarized by cohort using descriptive statistics.

Extent of Drug Exposure

The total number of doses of lenalidomide and everolimus (mg), and total number of treatment cycles delivered will be summarized by dose level using descriptive statistics.

Efficacy Endpoints

The secondary endpoint of the trial is response rate. The best overall response rate as defined by the proportion of subjects who have had a CR or PR will be summarized by dose level. Any subject treated in the expansion phase with overall response assessment of partial or complete response will have the response confirmed by repeat assessment no less than 4 weeks after the criteria for response are first met. The RR will be summarized by dose level using descriptive statistics along with a 95% confidence interval.

Pharmacokinetic Parameters

Serum concentration of study drug will be determined by a validated method according to assessment schedules. The pharmacokinetic parameters will be summarized using descriptive statistics.

The concentrations of everolimus, lenalidomide and their clinically significant metabolic product will be summarized by dose level using descriptive statistic. The mean concentration for each dose level will be plotted on scheduled sample time. The following pharmacokinetic parameters will be estimated and reported for each agent according to dose level.

$AUC_{0 \rightarrow t}$ Area under the concentration-time curve from the time of dosing to the time of the last observation; $AUC_{0 \rightarrow \infty}$ Area under the concentration-time curve from the time of dosing extrapolated to infinity; C_{max} Maximum serum concentration observed postdose; T_{max} Time point at which the C_{max} occurs; $t_{1/2}$ Elimination half-life, determined as $0.693/\lambda_z$.

Pharmacodynamic Correlates

The levels of mTOR pathway proteins, inflammatory cytokines and lymphocyte subsets at each specified time point will be reported in a descriptive manner for each dose schedule and analyzed by tumor type, when appropriate. Data will also be explored graphically. The PK and

pharmacodynamic data will be used to describe potential relationships between plasma levels of everolimus and or lenalidomide and changes in serum protein, toxicities, and tumor response.

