4.2.2 Secondary Endpoints

- The frequency of achieving a complete plus partial response or disease stabilization with the 2 drug combination by dose cohort. (Response will be assessed by cross sectional imaging after every 2 cycles and will be categorized according to RECIST 1.1 criteria)

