5.1 Overall design

This is a phase I, open-label, single institution, non-randomized study of escalating doses of daily, orally administered lenalidomide in combination with standard doses of everolimus, an orally available mTOR inhibitor. The trial is open to patients with advanced solid malignancies who have failed or are intolerant of available standard treatment options for their disease. Dose escalation will proceed in a modified Fibonacci 3+3 fashion with the requirement that dose escalation to the next level can only proceed if 0 of 3 or ≤ 1 of 6 patients experience a dose limiting toxicity (DLT). Four escalating dose cohorts and three deescalating dose cohorts will be used to evaluate different doses of lenalidomide and everolimus starting with the approved and or clinically relevant doses of both agents. The proposed starting dose level 1 is 10mg of lenalidomide (days 1 – 28) in combination with 10mg of everolimus (days 1 - 28) in a 28-day cycle. A serial de-escalation to 10mg of lenalidomide (days 1-21 of a 28 day cycle) and 5mg of everolimus will be carried out if DLT is observed in $\geq 33\%$ of patients enrolled to the starting dose cohort. The MTD is the highest dose level of lenalidomide and everolimus (up to a maximum dose of 25mg and 10mg respectively) at which $<33\%$ of the dose cohort experiences DLT after 1 cycle (28 days) of therapy. The established MTD will be the recommended dose for follow-up phase II study. To obtain preliminary clinical benefit of this combination, an expanded cohort of 15 patients with clear cell renal cell carcinoma, adenoidcystic carcinoma and neuroendocrine tumors will be treated at the define MTD. To allow for assessment of drug-drug interaction using PK analysis, lenalidomide will be administered alone on day 1 of the first cycle followed by both agents on day 2 cycle 1. Both drugs will be started simultaneously on day 1 of all subsequent cycles.

In addition, a parallel cohort of 9 additional patients with adenoicystic cancer will be treated at the RP2D. This is to enable us to obtain further evidence in support of the efficacy of this regimen in patients with adenoicystic cancer as observed in the limited number of patients with this cancer type who were enrolled in the escalation phase of the study.

Table 1

Dose Level	Lenalidomide (day 1 to 28)	Everolimus (day 1-28)	Patient Enrolment	Remarks
-2	10mg Days 1-21	5mg every other day	3 + 3	If DLT, study will close without defining a MTD

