-1	10mg Days 1-21	5mg	3 + 3	Deescalate to level -2 if ≥ 1 of 6 patients experience DLT, otherwise declare as MTD and expand the cohort
Starting Dose 1	10mg	5mg	3 + 3	Escalate to level 2 if 0 of 3 or 1 of 6 patients experience DLT, otherwise deescalate 1 level
2	15mg	5mg	3 + 3	Escalate to level 3 if 0 of 3 or 1 of 6 patients experience DLT, otherwise deescalate 1 level
3	20mg	5mg	3 + 3	Escalate to level 4 if 0 of 3 or 1 of 6 patients experience DLT, otherwise deescalate 1 level
4	25mg	5mg	3 + 3	if ≥ 1 of 6 patients experience deescalate 1 level, otherwise declare as MTD
5	25mg	10	3 + 3	if ≥ 1 of 6 patients experience deescalate 1 level, otherwise declare as MTD
MTD	TBD	TBD	15	Expanded cohort of 15 patients restricted to patients with renal cell carcinoma, adenoicystic carcinoma and neuroendocrine tumors

5.1.1 Blood Sample Collection:

Blood samples will be collected in heparinized green top tubes (3 mls for PK samples and 7 mls for PBMC collection), red top tube (7 mls to obtain serum sample for cytokine assay). PBMC will be purified using standard Ficoll-Paque gradient centrifugation according to the instructions of the manufacturer (Amersham Pharmacia, Uppsala, Sweden). All samples must be stored away within 1 hour of collection by refrigeration at -80°C until ready for assay.

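### The only response rate planned with a confidence interval is by dose level, which mixes tumour cohorts at the recommended dose and leaves the tumour-specific objectives without an estimate

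*Combined protocol and SAP*

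**What the plan says.** **How response is summarised.** Section 10.2, Efficacy Endpoints: "The RR will be summarized by dose level using descriptive statistics along with a 95% confidence interval". Section 4.2.2 agrees: the endpoint is the frequency of "complete plus partial response or disease stabilization with the 2 drug combination by dose cohort". Within section 10.2, tumour type is named as a stratum only for the pharmacodynamic markers, which are to be "reported in a descriptive manner for each dose schedule and analyzed by tumor type, when appropriate".

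**Who is treated at which dose.** Section 5.1 says of the trial as a whole: "The trial is open to patients with advanced solid malignancies who have failed or are intolerant of available standard treatment options". At the MTD, "an expanded cohort of 15 patients with clear cell renal cell carcinoma, adenoidcystic carcinoma and neuroendocrine tumors will be treated". The MTD row of Table 1 repeats the restriction: "Expanded cohort of 15 patients restricted to patients with renal cell carcinoma, adenoicystic carcinoma and neuroendocrine tumors". Section 5.1 then adds a parallel cohort of 9 further adenoid cystic patients at the RP2D, to follow up efficacy "as observed in the limited number of patients with this cancer type who were enrolled in the escalation phase of the study". The two doses are the same: "The established MTD will be the recommended dose for follow-up phase II study".

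**What the trial wants to know.** Section 4.1.2 sets two tumour-specific efficacy objectives: clinical benefit rate in an expanded renal cell cohort, and preliminary efficacy in an expanded adenoid cystic cohort.

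**What section 10.6 adds.** It gives an exact binomial power statement for 15 patients at the MTD (0% against 10%, significance level 0.05, power above 79%). It also sets a separate criterion for the adenoid cystic cohort, at least 3 objective responses in 9. The total of 45 is kept because escalation used only 21 patients.

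**The concern.** Selection by tumour type happens at one dose only. A table of response by dose level therefore compares a row made up largely of selected tumours with rows open to any solid tumour. A higher rate at the recommended dose could come from the drugs' dose, from the tumour mix, or from both, and the table cannot separate them.

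The same layout also fails the objectives. The expansion cohorts exist to give a first reading in named tumours, yet section 10.2 plans no rate and no interval for any of them. A signal in one tumour is diluted by the others at that dose, or a weak result in one is hidden by a strong one. The adenoid cystic denominator is loose as well: the 15-patient cohort admits that tumour too, while section 10.6 describes the expansion phase as confined to clear cell renal cell carcinoma.

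At stake is how a descriptive secondary endpoint is read when the phase II decision is taken.

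**Working it through.** **1. The plan's own figures reproduce.**
- Power for 15 patients: with a null rate of 0%, any single response rejects, so power at 10% is 1 − 0.9^15 = 0.794, as section 10.6 states.
- Total: 21 escalation + 15 + 9 = 45. The nine are thus separate from the 21.

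**2. Size and make-up of the row at the recommended dose, read literally.**
- Tumour-selected: 15 + 9 = 24.
- From escalation at that level: 3 to 6 (the 3 + 3 scheme, at most 6 per level).
- Row total: 24 + 3 = 27 to 24 + 6 = 30.
- Selected share: 24/27 = 89% to 24/30 = 80%.
- Left for all other dose levels together: 45 − 30 = 15 to 45 − 27 = 18 patients, none selected by tumour type.

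**3. What happens to an adenoid cystic signal.** Take 3 responses, all in the nine, which just meets the section 10.6 criterion. Intervals are exact (Clopper-Pearson) 95%.

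| Denominator | Rate | 95% CI |
|---|---|---|
| The 9 alone | 3/9 = 33% | 7.5% to 70.1% |
| Both expansion cohorts | 3/24 = 12.5% | 2.7% to 32.4% |
| Whole dose level, 6 from escalation | 3/30 = 10% | 2.1% to 26.5% |

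Section 10.2 plans none of these by cohort; on a literal reading it plans the last.

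**4. Can tumour mix alone produce a dose difference?** Assume no dose effect, a true rate of 33% in adenoid cystic carcinoma and 5% in everything else, and no adenoid cystic patients among the escalation patients. All three are assumptions.
- None of the 15 adenoid cystic, 6 from escalation: (9 × 0.33 + 21 × 0.05)/30 = 13%.
- All of the 15 adenoid cystic, 3 from escalation: (24 × 0.33 + 3 × 0.05)/27 = 30%.
- A lower level without adenoid cystic patients: 5%.

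So it can. The size depends heavily on the tumour mix in escalation. With assumed rates of 25% in adenoid cystic patients, 5% in other escalation patients and 5% to 10% in the 15:
- No adenoid cystic patients in escalation: recommended-dose row (6 × 0.05 + 15 × 0.05 + 9 × 0.25)/30 = 11.0%, or 13.5% with 10% in the 15. Against 5% at lower doses the ratio is 2.2 to 2.7.
- If instead the five salivary gland patients mentioned in section 3.4 were all adenoid cystic and spread evenly over the 21: escalation rate (16 × 0.05 + 5 × 0.25)/21 = 9.8%; recommended-dose row (6 × 0.098 + 15 × 0.05 + 9 × 0.25)/30 = 12.0%, or 14.5% with 10% in the 15. The ratio falls to about 1.2 to 1.5.

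**5. The 3-of-9 rule on the nine new patients.** The probability of at least 3 responses is 0.008, 0.053, 0.262 and 0.537 at true rates of 5%, 10%, 20% and 30%. If earlier responders were counted towards the three, contrary to the rule's wording, the probability at a true 10% would rise from 0.053 to 0.225 with one carried in (at least 2 of 9 needed) or 0.613 with two (at least 1 of 9 needed).

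**The case against.** **Section 10.6 already looks at cohorts.** This stands. The 15-patient power statement and the 3-of-9 rule are evaluations of response that are not by dose level. But a decision threshold and a power statement are not estimates, and section 10.2 supplies no cohort rate or interval to go with them.

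**Pooling is an inference.** Table 1 lists the MTD as its own entry with 15 patients, apart from levels 1 to 5, so a table by dose level might show that cohort alone. This stands in part: the 27-to-30-patient row is the literal and likely reading, not a certain one. Table 1 has no entry for the nine, however. They either join another row or have none, and the 15 still mix three tumours.

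**Readers might infer that the patients who prompted the adenoid cystic cohort also count in its test.** The documents do not support that. Section 5.1 calls the nine additional, and 21 + 15 + 9 = 45 leaves the prompting patients among the 21. Whether any of them fall in the recommended-dose row depends on the doses they received, which the available text does not give.

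**Readers might infer a two- to threefold spurious dose effect.** That needs escalation to contain no adenoid cystic patients, and section 5.1 says it did contain some. Confounding is heavy but not complete.

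**The table is descriptive.** No dose-response test is planned, and lower rows of 3 to 6 patients are too small to show a trend (exact interval 0% to 71% for 0/3, 0% to 46% for 0/6). Individual listings would also let someone rebuild rates by tumour. All true, and this limits the harm. It does not explain why the plan should leave the tumour-specific objectives to be rebuilt afterwards.

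**Conclusion.** The point holds as a gap in the planned estimates. The only response rate with an interval is by dose level. On a literal reading, 80% to 89% of the recommended-dose row is tumour-selected, and neither efficacy objective in section 4.1.2 receives an estimate. The clearest measure is the 3-of-9 example: 10% (2.1% to 26.5%) by dose level against 33% (7.5% to 70.1%) by cohort. It assumes 6 escalation patients at that dose and no other responder there.

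Tumour mix can produce a difference between dose rows without any dose effect, but no single size can be given. It depends on assumed rates and on the tumour mix in escalation. The section 10.6 rule for adenoid cystic carcinoma is not compromised. This is a worthwhile, inexpensive improvement to a descriptive secondary analysis; it does not threaten the primary MTD objective.

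**What to change.** In section 10.2, replace the single summary by dose level with three:

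1. Response by dose level for escalation patients only.
2. For each expansion cohort separately, response rate with an exact 95% confidence interval. Break the 15-patient cohort down by tumour type as well, and give clinical benefit rate with its interval for renal cell carcinoma.
3. Adenoid cystic patients from escalation shown separately, outside the estimate for the nine.

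It would help to add one sentence confirming that the 3-of-9 rule counts only the nine new patients, and one saying which expansion cohort an adenoid cystic patient joins. Section 10.6's description of the expansion population should be reconciled with section 5.1 and Table 1.

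Cost: wording only, with no new data or patients. Each row is smaller, so its interval is wider, and the breakdown of the 15 by tumour type will be very imprecise.

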10.3 Statistical Methodology

All data will be listed individually by subject. Continuous variables will be summarized using descriptive statistics: mean, standard deviation, median, and minimum and maximum values. Categorical variables will be summarized using number of subjects and proportion expressed as percentage. Baseline value for any specified variable is the last valid measurement before the administration of the study drug. Unless otherwise indicated, statistical significance will be declared if the two-sided p value is ≤ 0.05 .

The estimation of pharmacokinetic parameters will be performed using WinNonlin® Version 5.0 or higher. All statistical analyses will be performed using SAS® Version 9.13 or higher.

Changes in immunological markers between baseline and C2D1 samples will be compared for each patient and for each dose cohort. In addition, mTOR pathway protein expression in baseline diagnostic biopsy samples will be assessed by Immunohistochemistry (IHC) and correlated with response. The dynamic changes in biomarker expression before and after one cycle of treatment with the drug combination will be summarized using summary statistics mean and standard deviation. Comparisons between the two time points will be presented graphically and subjected to statistical analysis using the Pearson's correlation coefficient.

Missing Data Handling

Unresolved missing data may be imputed when the analysis integrity is affected. The conservative principle will be used for data imputation. For example, if an adverse event onset day is missing but the adverse event onset year and month can not exclude this adverse event as a TEAE, the adverse event will be flagged as a TEAE.

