4.1.3 Correlative Objectives

- Correlate mTOR pathway protein expression in archival diagnostic tumor tissue with the clinical activity of everolimus
- Determine the predictive ability of changes in inflammatory and immunologic markers in paired blood samples as pharmacodynamic evidence of target modulation by escalating doses of lenalidomide
- Correlate changes in level of cathepsin G in plasma with escalating doses of lenalidomide and with incidence of venous thromboembolism
- Correlate myb protein expression with the efficacy of the combination of everolimus and lenalidomide in patients with adenoidcystic carcinoma.
- Assess the predictive value of myb gene alteration in patients with adenoidcystic cancer

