4.2.3 Correlative Endpoints

- Immunoscore of mTOR pathway protein expression (S6, pS6, 4E-BP1, p-4E-BP1, eI4F, Akt, pAkt, raptor, rictor, PRAS40, mSin1, FKBP38, and IRS-1 and HIF1- α) in archival biopsy sample for all patients and in paired fresh tumor biopsy specimens in up to 15 patients treated at P2RD if a separate informed consent is obtained.
- Immunoscore of myb protein expression in archival tissue samples in patients with adenoidcystic cancer.
- Serum level of inflammatory and immunologic markers (IL-6, IL-8, IL-12, IFN- γ , TNF- α , sIL-2R- α , CD4+ and CD8+ T-cell, NK cell and Treg cells); markers of angiogenesis (circulating VEGF and soluble VEGFR) and level of the potent platelet aggregator, cathepsin G, will be performed in serial blood samples collected at baseline, at the end of cycle 1 and at the time of disease progression or first diagnosis of venous thromboembolism (in the case of cathepsin G) and correlated with lenalidomide therapy by dose cohort.

5 Investigational Plan

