5.3.2 CLINICAL PHARMACOLOGY

Mechanism of Action

Everolimus is an inhibitor of mTOR (mammalian target of rapamycin), a serine-threonine kinase, downstream of the PI3K/AKT pathway. The mTOR pathway is dysregulated in several human cancers. Everolimus binds to an intracellular protein, FKBP-12, resulting in an inhibitory complex formation and inhibition of mTOR kinase activity. Everolimus reduced the activity of

S6 ribosomal protein kinase (S6K1) and eukaryotic elongation factor 4E-binding protein (4E-BP), downstream effectors of mTOR, involved in protein synthesis. In addition, everolimus inhibited the expression of hypoxia-inducible factor (e.g., HIF-1) and reduced the expression of vascular endothelial growth factor (VEGF). Inhibition of mTOR by everolimus has been shown to reduce cell proliferation, angiogenesis, and glucose uptake in in vitro and/or in vivo studies.

Pharmacodynamics

QT/QTc Prolongation Potential - In a randomized, placebo-controlled, crossover study, 59 healthy subjects were administered a single oral dose of AFINITOR (20 mg and 50 mg) and placebo. There is no indication of a QT/QTc prolonging effect of AFINITOR in single doses up to 50 mg. Markers of protein synthesis show that inhibition of mTOR is complete after a 10 mg daily dose.

Pharmacokinetics

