Everolimus has no genotoxicity or carcinogenicity potential. All significant adverse events observed in preclinical toxicology studies with everolimus in mice, rats, monkeys and minipigs were consistent with the anticipated pharmacological action as an antiproliferative and immunosuppressant and at least in part reversible after a two or four week recovery period, with the exception of the changes in male reproductive organs, most notably testes. Ocular effects (lenticular disorders) observed in rats were not observed in any other species and are considered to be a species-specific disorder. The known pharmacokinetic half-life of 30 hours in patients, and the prolonged pharmacodynamic effect of several days demonstrated preclinically, justified initial use of a weekly regimen in patients as a means of investigating safety at doses higher than those used in previous transplant studies. At the same time, analysis of changes in a non-tumoral, blood borne biomarker of activity in patients permitted pharmacokinetic-pharmacodynamic modeling with extrapolation from preclinical findings to predict the likely effect of everolimus on its intracellular target in tumors, at different doses for both the weekly and daily regimens.

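### The correlative objective is marker change driven by escalating lenalidomide, but Section 10.3 specifies no analysis that estimates a lenalidomide dose effect

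*Combined protocol and SAP*

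**What the plan says.** The Synopsis and Section 4.1.3 make change in inflammatory and immunologic blood markers a correlative objective, to be read "as pharmacodynamic evidence of target modulation by escalating doses of lenalidomide". Section 4.2.3 lists cytokines, T-cell, NK and Treg counts, angiogenesis markers and cathepsin G, and says they will be "correlated with lenalidomide therapy by dose cohort". It gives no model, dose variable or test.

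Section 10.3 is where a method would be expected. It says "Changes in immunological markers between baseline and C2D1 samples will be compared for each patient and for each dose cohort". It then summarises biomarker change "before and after one cycle of treatment with the drug combination" by mean and standard deviation, and adds: "Comparisons between the two time points will be presented graphically and subjected to statistical analysis using the Pearson's correlation coefficient". It contains no analysis across lenalidomide doses and no term for everolimus.

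Three other parts of the protocol bear on this:

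- **Dosing (Sections 5.1 and 5.6.2).** Lenalidomide is given alone on day 1 of cycle 1 only, and everolimus starts on day 2. No on-treatment marker sample is scheduled before everolimus begins.
- **Dose levels (Table 1).** Levels 1 to 4 give lenalidomide 10, 15, 20 and 25 mg, all with everolimus 5 mg. Level 5 keeps lenalidomide at 25 mg and raises everolimus to 10 mg.
- **Everolimus pharmacology (Section 5.3.5).** Preclinical adverse findings are described as "consistent with the anticipated pharmacological action as an antiproliferative and immunosuppressant".

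**The concern.** The objective asks whether more lenalidomide moves the markers more. A baseline-to-follow-up comparison inside one cohort asks whether the markers moved at all in patients taking two drugs. By the protocol's own account the second drug suppresses the immune system, so an immune-cell or cytokine change at a given level cannot be assigned to lenalidomide. Replacing Pearson with a correct paired test would not cure this, because a paired test still answers the question about any change.

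The correlation by dose cohort in Section 4.2.3 comes closer. Run over all levels without an everolimus term, however, it would mix the level 5 everolimus increase into the lenalidomide slope.

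Section 10.2 offers one other way to separate the drugs, by relating plasma levels of each drug to marker changes. That way is closed: Section 5.1.2 and Appendix D say that no PK work is done in this study. The contrast between dose levels is what remains, and it is unspecified. At stake is a correlative objective that goes unanswered, or is answered with a combination effect. The MTD and safety objectives are unaffected.

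**Working it through.** The documents give no effect size, SD, power or sample size for the marker analysis, so there is no planned figure to reproduce. All effects below are assumptions, in units of the SD of the change score.

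**Inputs.** Two-sided alpha 0.05 (Section 10.3). 21 escalation patients (Section 10.6), split 3/3/3/6/6 over levels 1-5; the split is assumed. Doses from Table 1. No lenalidomide effect, except in step 4.

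**1. Pearson between time points.** Adding a constant c to every follow-up value leaves r unchanged: corr(x, y + c) = corr(x, y). In a numerical check r was 0.438 both with and without a 3 SD shift. The one method named for the two time points does not test change, and still less a dose effect.

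**2. Pre/post comparison.** Suppose a paired t test is used (the plan does not name one). With a shift d common to all patients, the noncentrality is d√n on n − 1 degrees of freedom.

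| Shift | One cohort, n=3 | One cohort, n=6 | Pooled, n=21 |
|---|---|---|---|
| 0.5 SD | 8% | 17% | 59% |
| 1 SD | 18% | 51% | 99% |

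For the pooled test the noncentrality is 0.5 × √21 = 2.29, or √21 = 4.58 at 1 SD. The chance that at least one of the five cohorts is significant is 47% and 87%. These belong against 1 − 0.95^5 = 22.6% at zero shift, not against 5%.

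**3. Slope on lenalidomide dose, levels 1-4.** A shift common to all patients goes into the intercept, so rejection stays at 5%. Simulation gave 4.8% to 5.1% for common shifts from 0 to 1.5 SD and cohorts of 3, 4 or 6.

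**4. Power of that slope.** There are 15 patients at 10, 15, 20 and 25 mg (3, 3, 3, 6). Mean dose = 285/15 = 19. Sxx = 3(81) + 3(16) + 3(1) + 6(36) = 510. If the marker moves by D SD across the 15 mg range, the noncentrality is (D/15)√510 = 1.51 D on 13 degrees of freedom. Power is 29%, 55% and 79% for D = 1, 1.5 and 2.

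**5. Slope over all levels, no everolimus term.** Let doubling everolimus move the marker by 0.5 to 1 SD.

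- With six patients at level 5, the mean dose is 435/21 = 20.7 and Sxx = 664. The spurious slope over 15 mg at a 1 SD effect is 15 × 6 × 4.29/664 = 0.58 SD. The test rejects about 7% to 12% of the time.
- With 30 patients there (6 + 15 + 9, which makes the total 45), the mean dose is 1035/45 = 23 and Sxx = 870. The spurious slope is 15 × 30 × 2/870 = 1.03 SD. The test rejects about 16% to 46% of the time.

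The second case assumes that both expansion cohorts are treated at level 5. The available text does not say which level was chosen.

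**The case against.** A reader might infer that the plan tests for change from any cause and will read an everolimus effect as lenalidomide target modulation. The documents do not support that. The Section 10.3 sentence names no test, and comparing changes for each patient cannot be one. The paired t tests above are an assumption of this review. Section 10.3 attributes change to the combination, and Section 10.2 reports these data descriptively by dose schedule. Misattribution is a risk created by the wording of the objective, not a stated rule. A rejection in step 2 is also a correct finding that the marker moved; it is wrong only if credited to lenalidomide.

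It is also fair to say that a dose comparison is intended. Section 4.2.3 states one, the Synopsis reports mean change by cohort, and the Section 10.3 sentence can be read as a comparison across cohorts. This stands: what is missing is the method, not the intention.

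The slope is no clean answer either. Section 5.6.1 assigns patients to levels in order of entry, so dose is confounded with calendar time and case mix. A linear drift of 1 SD across levels 1-4 with no drug effect has the same noncentrality as a real 1 SD effect, and would be declared significant 29% of the time.

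Finally, the Section 10.3 sentence concerns immunological markers. Section 4.2.3 classes VEGF with the angiogenesis markers, so the protocol's statement that everolimus lowers VEGF expression bears on Section 4.2.3 and not on that sentence. The argument here rests on immunosuppression.

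**Conclusion.** The point holds as an unspecified analysis. The objective concerns a lenalidomide dose effect, Section 4.2.3 promises a correlation with dose cohort, and nothing in Section 10.3 estimates it. Under the stated assumptions a pooled pre/post test would respond to a common shift 59% to 99% of the time with lenalidomide inert, against 5% for the level 1-4 slope. Carelessly including level 5 costs little with six patients there (7% to 12%) and more with 30 (16% to 46%).

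Two conditions limit this. First, constant everolimus over levels 1-4 rests on Table 1. The Synopsis and Section 5.6.2 agree with its 5 mg starting dose, while the text of Section 5.1 gives 10 mg at the starting level. Second, the follow-up sample may not exist at the analysed time. Section 10.3 uses C2D1, Section 4.2.3 uses the end of cycle 1, and the Section 2 grid marks day 1 of even-numbered cycles. Footnote 11 to that grid and Appendix D instead tie the samples to restaging (C3D1, and in Appendix D also C5D1).

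This is an exploratory objective in a phase I trial, so the change should be made but is not critical to the trial's main conclusions.

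**What to change.** First reconcile the on-treatment sampling time across Sections 2, 4.2.3 and 10.3 and Appendix D, and the starting everolimus dose between the Section 5.1 text and Table 1, the Synopsis and Section 5.6.2. Then replace the immunological-marker sentence in Section 10.3 with wording such as:

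> For each blood marker, the log-scale change from baseline to [one named on-treatment time point] will be regressed on assigned lenalidomide dose, adjusted for the baseline value, in patients treated at levels with the same everolimus dose (levels 1-4 of Table 1). The slope will be reported with its 95% confidence interval. Patients at the other everolimus dose enter a sensitivity analysis that adds an everolimus term. Change within a cohort is descriptive and is attributed to the combination. Because cohorts were filled sequentially without randomisation, the slope is exploratory.

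State also whether expansion patients enter. If their dose falls within levels 1-4, add a tumour-type term. Keep Pearson between time points, if at all, only as a description of how values track.

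The cost is a wording change and one regression per marker, with no added patients or samples beyond those planned. The drawbacks are the modest power in step 4 (adjusting for baseline uses one further degree of freedom) and the drift and case-mix confounding, which no model on these data removes.
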